APPENDIX 7. STUDY GOVERNANCE CONSIDERATIONS

Regulatory and Ethical Considerations

- This study will be conducted in accordance with the protocol and with the following:
 - Consensus ethical principles derived from international guidelines including the Declaration of Helsinki and Council for International Organizations of Medical Sciences (CIOMS) International Ethical Guidelines
 - Applicable ICH Good Clinical Practice (GCP) Guidelines
 - Applicable laws and regulations
- The protocol, protocol amendments, ICF, Investigator Brochure, and other relevant documents (eg, advertisements) must be submitted to an IRB by the investigator and reviewed and approved by the IRB before the study is initiated.
- Any amendments to the protocol will require IRB approval before implementation of changes made to the study design, except for changes necessary to eliminate an immediate hazard to study patients.
- The investigator will be responsible for the following:
 - Providing written summaries of the status of the study to the IRB annually or more frequently in accordance with the requirements, policies, and procedures established by the IRB
 - Notifying the IRB of SAEs or other significant safety findings as required by IRB procedures
 - Providing oversight of the conduct of the study at the site and adherence to requirements of 21 Code of Federal Regulations (CFR), ICH guidelines, the IRB, European regulation 536/2014 for clinical studies (if applicable), and all other applicable local regulations

Financial Disclosure

Investigators and sub-investigators will provide the sponsor with sufficient, accurate financial information as requested to allow the sponsor to submit complete and accurate financial certification or disclosure statements to the appropriate regulatory authorities. Investigators are responsible for providing information on financial interests during the course of the study and for 1 year after completion of the study.

Informed Consent Process

- The investigator or his/her representative will explain the nature of the study to the patient or his/her legally authorized representative and answer all questions regarding the study.
- Patients must be informed that their participation is voluntary. Patients or their legally authorized representative will be required to sign a statement of informed consent that

meets the requirements of 21 CFR 50, local regulations, ICH guidelines, Health Insurance Portability and Accountability Act requirements, where applicable, and the IRB or study center.

- The medical record must include a statement that written informed consent was obtained before the patient was enrolled in the study and the date the written consent was obtained. The authorized person obtaining the informed consent must also sign the ICF.
- Patients must be re-consented to the most current version of the ICF(s) during their participation in the study.
- A copy of the ICF(s) must be provided to the patient or the patient's legally authorized representative.

Patients who are rescreened are required to sign a new ICF.

Data Protection

- Patients will be assigned a unique identifier by the sponsor. Any patient records or datasets that are transferred to the sponsor will contain the identifier only; patient names or any information which would make the patient identifiable will not be transferred.
- The patient must be informed that his/her personal study-related data will be used by the sponsor in accordance with local data protection law. The level of disclosure must also be explained to the patient who will be required to give consent for their data to be used as described in the informed consent.
- The patient must be informed that his/her medical records may be examined by Clinical Quality Assurance auditors or other authorized personnel appointed by the sponsor, by appropriate IRB members, and by inspectors from regulatory authorities.

Data Quality Assurance

All patient data relating to the study will be recorded on printed or eCRF unless transmitted to the sponsor electronically (eg, electronic diary). The Investigator is responsible for verifying that data entries are accurate and correct by physically or electronically signing the eCRF.

The Investigator must maintain accurate documentation (source data) that supports the information entered in the eCRF.

The Investigator must permit study-related monitoring, audits, IRB review and regulatory agency inspections and provide direct access to source data documents.

Monitoring details describing strategy (eg, risk-based initiatives in operations and quality such as Risk Management and Mitigation Strategies and Analytical Risk-Based Monitoring), methods, responsibilities and requirements, including handling of noncompliance issues and monitoring techniques (central, remote or on-site monitoring) are provided in the Monitoring Plan.

The Sponsor or designee is responsible for the data management of this study including quality checking of the data.

The Sponsor assumes accountability for actions delegated to other individuals (eg, Contract Research Organizations).

Study monitors will perform ongoing source data verification to confirm that data entered into the eCRF by authorized site personnel are accurate, complete, and verifiable from source documents; that the safety and rights of patients are being protected; and that the study is being conducted in accordance with the currently approved protocol and any other study agreements, ICH GCP, and all applicable regulatory requirements.

Records and documents, including signed ICFs, pertaining to the conduct of this study must be retained by the Investigator for at least 2 years after the last marketing application approval or 2 years after formal discontinuation of the clinical development of the investigational product or according to applicable regulatory requirement(s). If the Investigator withdraws from the responsibility of keeping the study records, custody must be transferred to a person willing to accept the responsibility. The Sponsor must be notified immediately by telephone or e-mail and the notification confirmed in writing if a custodial change occurs.

Source Documents

Source documents provide evidence for the existence of the patient and substantiate the integrity of the data collected. Source documents are filed at the Investigator's site.

Data entered in the eCRF that are transcribed from source documents must be consistent with the source documents or the discrepancies must be explained. The Investigator may need to request previous medical records or transfer records, depending on the study. Also, current medical records must be available.

Any electronic study data are to be entered into a secure, validated data processing system and a backup maintained. Any changes to electronic study data will be documented.

Study and Site Closure

The sponsor or designee reserves the right to close the study site or terminate the study at any time for any reason at the sole discretion of the sponsor. Study sites will be closed upon study completion. A study site is considered closed when all required documents and study supplies have been collected and a study-site closure visit has been performed.

The investigator may initiate study-site closure at any time, provided there is reasonable cause and sufficient notice is given in advance of the intended termination.

Reasons for the early closure of a study site by the sponsor or investigator may include but are not limited to:

For study termination:

- Discontinuation of further study intervention development.

For site termination:

- Failure of the investigator to comply with the protocol, the requirements of the IRB or local health authorities, the sponsor's procedures, or GCP guidelines.

Inadequate or no recruitment (evaluated after a reasonable amount of time) of participants by the investigator.

- Total number of participants included earlier than expected.

If the study is prematurely terminated or suspended, the sponsor shall promptly inform the investigators, the IECs/IRBs, the regulatory authorities, and any contract research organization(s) used in the study of the reason for termination or suspension, as specified by the applicable regulatory requirements. The investigator shall promptly inform the participant and should assure appropriate participant therapy and/or follow-up.

Publication Policy

All information regarding setmelanotide supplied by the Sponsor to the Investigator or generated as a result of any clinical studies is privileged and confidential information belonging to the Sponsor. The Investigator agrees to use Sponsor's confidential information solely to accomplish the study and will not use such information for any other purposes without the prior written consent of Rhythm. It is understood that there is an obligation to provide the Sponsor with complete and accurate data obtained during the study. The information obtained from the clinical study will be used towards the development of setmelanotide and may be disclosed by Rhythm to regulatory authority(ies), other investigators, corporate partners, or consultants as required.

It is anticipated that the results of this study may be presented at scientific meetings and/or published in a peer reviewed scientific or medical journal. The Sponsor generally supports publication of multicenter studies initially in their entirety and not as individual site data. A coordinating investigator will be designated.

Subsequently, individual Investigators may publish results from the study in compliance with their agreement with the Sponsor.

A pre-publication manuscript is to be provided to Rhythm at least 30 days prior to the submission of the manuscript to a publisher. Similarly, the Sponsor will provide any company-prepared manuscript to the Investigators for review at least 30 days prior to submission to a publisher. All publications and presentations must be approved in writing by Rhythm before public disclosure.

Authorship will be determined by mutual agreement and in line with International Committee of Medical Journal Editors authorship requirements.

APPENDIX 8. GUIDANCE ON STUDY CONDUCT DURING THE COVID-19 (CORONAVIRUS) PANDEMIC

The Coronavirus Disease 2019 (COVID-19) pandemic could impact the conduct of this clinical study for several reasons, including: self-isolation/quarantine by patients and study-site personnel; travel restrictions/limited access to public places, including hospitals; and reassignment of site personnel to critical tasks.

In accordance with recent health authority guidance, the Sponsor is providing temporary considerations for study conduct in the event of disruption of the study. This guidance does not supersede any local or government requirements or the clinical judgment of the investigator. If at any time a patient's safety is considered to be at risk, study intervention will be discontinued, and study follow-up will be conducted.

If COVID restrictions are imposed on or by the study site and the site cannot fully carry out normal operations, the following measures are recommended on a temporary basis during the COVID-19 pandemic:

- Where possible, every effort should be made to complete all protocol-required assessments. In place of a required site visit, a qualified healthcare provider could perform study-related procedures as per the Schedule of Events via a home visit, including but not limited to collection of body weight, vital signs, physical examinations, electrocardiograms (ECGs), recording of adverse events (AEs), collection of blood and urine samples. Most efficacy assessments could potentially be done off site. Investigators should use their clinical judgment to determine whether a patient can continue study treatment in the absence of on-site clinic visits, or consider alternatives such as temporary treatment interruption or study discontinuation.
- All protocol-required assessments missed due to COVID restrictions should be documented in detail within the patients' source documents and should be clearly designated as "COVID-19 RELATED". It must be documented if a site visit is instead conducted remotely. Source documentation should detail how each assessment was collected (eg, remote vs. on-site, central vs. local laboratory, vital signs taken at home by caretaker vs. delegated in-home nursing, etc).
- If applicable, discontinuations of study interventions and withdrawal from the study due to disruption of study conduct by the pandemic should be documented with the prefix "COVID-19 RELATED" in the case report form (CRF).

## 1 List of Abbreviations and Definition of Terms

Abbreviation	Description
AE	Adverse Event
ATC-3	Anatomical Therapeutic Chemical 3rd level
ATC-4	Anatomical Therapeutic Chemical 4th level
BMI	Body Mass Index
CDISC	Clinical Data Interchange Standards Consortium
CI	Confidence Interval
CSR	Clinical Study Report
CS	Clinically Significant
CTCAE	Common Terminology Criteria for Adverse Events
C-SSRS	Columbia-Suicide Severity Rating Scale
DAO	Data as Observed
DXA	Dual-Energy X-Ray
ECG	Electrocardiogram
EOS	End of Study
EQ-5D	EuroQol-Five Dimension
eCRF	Electronic Case Report Form
FAS	Full Analysis Set
FCS	Fully Conditional Specification
HO	Hypothalamic Obesity
HR	Heart Rate
ICH	International Conference on Harmonization
IWQOL-Lite-CT	Impact of Weight on Quality of Life-Lite-Clinical Trials
LOCF	Last Observation Carried Forward
MAR	Missing at Random
MCMC	Markov Chain Monte Carlo
MedDRA	Medical Dictionary for Regulatory Activities
MI	Multiple Imputation
NCS	Non-clinically Significant
OC	Observed Counts
PHQ	Patient Health Questionnaire
PP	Per-Protocol Set
PT	Preferred Term
SAE	Serious Adverse Event
SAP	Statistical Analysis Plan
SC	Subcutaneously
SD	Standard Deviation
SF	Short Form

Abbreviation	Description
SoA	Schedule of Activities
SOC	System Organ Class
TEAE	Treatment-Emergent Adverse Event
WHO	World Health Organization

## 2 Introduction

This statistical analysis plan (SAP) describes the efficacy and safety summaries and analyses that will be performed for Study RM-493-030, *A Phase 2, Open-Label 20-Week Study to Evaluate the Safety and Efficacy of Setmelanotide in Patients with Hypothalamic Obesity* and is based on the study protocol Version 2.0 dated 9 September 2021 and study Electronic Case Report Forms (eCRFs) Version 1.0 dated 18 March 2021.

## 3 Study Objectives and Overall Design

### 3.1 Study Objectives

#### 3.1.1 Primary Objective

The primary objective of this study is to evaluate the change in body weight in response to setmelanotide administered subcutaneously (SC) daily in patients with Hypothalamic Obesity (HO).

#### 3.1.2 Secondary Objective(s)

The secondary objectives of this study are to evaluate changes in parameters of body weight, body mass index (BMI), waist circumference, and hunger in response to setmelanotide in patients with HO and to evaluate the safety and tolerability of setmelanotide in patients with HO.

### 3.2 Overall Design

This is a Phase 2, multi-center, open-label, proof of concept study designed to assess the effect of setmelanotide on weight loss on a population affected by HO. Approximately 15 patients aged 6 to 40 years, inclusive, are planned to be enrolled across approximately 3-5 clinical sites in the United States.

Patients will first enter the Screening Period, during which they will be assessed for eligibility and complete all screening procedures as described in the Schedule of Activities (SoA) ([Section 16.1](#)). Individuals who do not meet the criteria for participation in this study (screen failure) may be eligible for rescreening at a later date, depending on the reason for the initial screen failure and provided enrollment is still open. If a patient is approved for rescreening by the Sponsor, the rescreened patient should be assigned the same Screening number as for the initial screening. Up to 3 screenings per patient are allowed (2 screening failures).

Patients who are determined to be eligible, based on screening assessments, will return to the clinic for the Baseline Visit (Visit 2) and receive their first setmelanotide dose. Patients will return to the study center for Visits 3, 4, and 5 (Weeks 4, 8, and 12, respectively), with each of these visits conducted approximately 4 weeks apart. All patients will return to the study center at Week 16 (Visit 6) and receive the last setmelanotide injection. After completion of Visit 6, participation in the current study will then conclude in one of the following 2 ways:

1. Patients meeting the primary endpoint meeting may be eligible to be enrolled in a separate extension study, Rhythm Study RM-493-022, under which auspices the patient will continue to receive setmelanotide.
2. Patients who do not meet the primary endpoint or elect not to continue setmelanotide are to discontinue setmelanotide at Visit 6 and return for an End-of-Study Visit (Visit 7) 4 weeks thereafter for a final safety review under the auspices of the current study.

### **3.2.1 Study Patients**

The study is planned to enroll ~15 patients affected by HO, with ~5-10 patients aged >12 years, and up to 10 patients between 6 and 12 years.

## **3.3 Treatments and Assignment to Treatments**

All patients will receive setmelanotide in this study. The starting setmelanotide dose is dependent on patient age at the time of Visit 2 (Day 1); however, for all patients, the setmelanotide dose will be titrated to a final dose of 3.0 mg/day (initial titration phase), as follows:

### **Patients aged 6 to <16 years, inclusive**

- Starting at Baseline (Day 1; Visit 2) through approximately Day 14, patients will receive setmelanotide 1.0 mg/day.
- Starting at approximately Day 15 through 28, patients will receive setmelanotide 2.0 mg/day.
- Starting on approximately Day 29 (Visit 3), patients will receive setmelanotide 3.0 mg/day; patients will continue to receive setmelanotide 3.0 mg/day for 12 weeks.

### **Patients aged ≥16 years, inclusive**

- Starting at Baseline (Day 1; Visit 2) through approximately Day 14, patients will receive setmelanotide 2.0 mg/day.
- Starting at approximately Day 15, patients will receive setmelanotide 3.0 mg/day; patients will continue to receive setmelanotide 3.0 mg/day for 14 weeks.

### 3.4 Determination of Sample Size

The objective of this study is to evaluate safety and preliminary efficacy on weight loss in patients with HO. The primary endpoint is the proportion of patients who achieve at least 5% BMI reduction from baseline at ~16 weeks of treatment with setmelanotide. Given the exploratory nature of the study, the sample size is primarily driven by clinical considerations, with the considerations of statistical testing. It is planned to enroll ~5-10 patients aged >12 years, and up to 10 patients between 6 and 12 years. With 10 patients aged >12 years and up to 10 patients aged 6 to 12 years, at 1-sided 0.05 significance level, the study provides ~90% power to reject the null hypothesis that the true response rate is less than historical control rate of 5%, assuming a 40% target response rate in setmelanotide.

### 3.5 Patient Assessments

#### 3.5.1 Vital Signs

Vitals signs include:

- Height (cm)
- Weight (kg)
- Waist circumference (cm)
- Temperature (C)
- Heart Rate (beats/min)
- Systolic Blood Pressure (mmHg)
- Diastolic Blood Pressure (mmHg)
- Respiratory Rate

Vital signs will be assessed from screening and at every post-baseline visit. Patients 18 years or older will only have height measured at screening. Height, weight, heart rate, systolic blood pressure, and diastolic blood pressure will be measured in triplicates at each visit. In addition to the individual measurements the above items will be aggregated into a mean value per visit (i.e. mean of all height measurements).

#### 3.5.2 Body Composition

Patients will have body composition measurements performed by dual-energy X-ray absorptiometry (DXA) at baseline and Visit 6. The following measures will be obtained by DXA scan:

- Total fat mass (g or kg)
- Lean muscle (g or kg)
- Total body mass (g or kg)

- Total body bone mineral density (g, kg, g/cm^2, or kg/m^2)
- Android/gynoid fat ratio

For the purpose of analysis, all applicable body composition measurements will be standardized to the unit of kilograms, or kg/m^2 for total body bone mineral density, using the following formula:

$$Kg = \frac{g}{1000}$$

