### 8.5 Body Composition

Dual-energy X-ray absorptiometry measurements (described in [Section 3.5.2](#)) at baseline, Visit 6, and the changes from baseline to Visit 6 will be summarized using descriptive statistics.

A data listing will be created to present all DXA assessments. The listing will show the assessment date, DXA assessment, indicator measurement was not done (if applicable), measurement value, and the change from baseline.

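### SAP 3.5.2 divides bone mineral density by 1000 to reach kg/m², but 1 g/cm² equals 10 kg/m², so values converted as written are 10,000 times too small

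*SAP*

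**What the plan says.** SAP 3.5.2 (Body Composition) lists five DXA measures: total fat mass, lean muscle, total body mass, bone mineral density and the android/gynoid fat ratio. The three masses may be recorded in g or kg. The density item reads "Total body bone mineral density (g, kg, g/cm 2 , or kg/m 2", so four recorded units are allowed.

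The section then says that "all applicable body composition measurements will be standardized to the unit of kilograms", with kg/m² as the target "for total body bone mineral density, using the following formula". A single formula follows, Kg = g/1000. No area conversion appears there or elsewhere in the SAP.

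SAP 8.5 uses the results: the DXA measurements "at baseline, Visit 6, and the changes from baseline to Visit 6 will be summarized using descriptive statistics", and a listing shows each value and its change from baseline. SAP 10.5 also points to section 3.5.2, alongside 3.5.1, when it defines the vital signs to be summarized.

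**The concern.** The formula converts mass. Bone mineral density is mass per area, and going from g/cm² to kg/m² changes both the numerator and the denominator. The sentence names density and sends it through the mass formula, so a programmer who follows the SAP would label as kg/m² a number that is not in kg/m².

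Two things are at stake. If every site records g/cm², all reported densities and absolute changes are on the wrong scale by one constant factor. If some sites record g/cm² and others kg/m², which the SAP allows, converted and unconverted values are pooled on different scales, and the mean, SD and change from baseline cannot be interpreted.

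The g and kg options add a further gap. They are mass units, and the SAP gives no route from them to kg/m².

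**Working it through.** **Inputs.** Allowed recorded units for density: g, kg, g/cm², kg/m² (SAP 3.5.2). Target unit: kg/m² (SAP 3.5.2). Conversion: divide by 1000 (SAP 3.5.2). Unit definitions: 1 g = 0.001 kg; 1 cm² = (0.01 m)² = 0.0001 m².

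**The SAP's formula.** For a mass, kg = g/1000 is correct. Applied to a density of 1.0 g/cm², it gives 1.0/1000 = 0.001.

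**Correct conversion.** 1 g/cm² = 0.001 kg / 0.0001 m² = 10 kg/m².

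**Ratio.** 10 / 0.001 = 10,000, the same for every value. The densities below are assumed for illustration:

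| Recorded (g/cm²) | SAP formula | Correct (kg/m²) | Ratio |
|---|---|---|---|
| 0.8 | 0.0008 | 8 | 10,000 |
| 1.0 | 0.001 | 10 | 10,000 |
| 1.2 | 0.0012 | 12 | 10,000 |

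**Is dividing by 1000 right for any listed density unit?**
- g/cm²: no. The factor is ×10; dividing by 1000 gives kg/cm².
- kg/m²: already in the target unit, so no conversion is needed.
- g or kg: masses. Reaching kg/m² needs a bone area, which is not among the listed DXA measures.
- g/m² is the unit for which the formula would be right, and it is not on the list.

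**Change from baseline.** Assume 1.00 g/cm² at baseline and 1.02 at Visit 6. The SAP formula gives 0.02/1000 = 0.00002; the correct change is 0.02 × 10 = 0.2 kg/m². Percent change is 2% either way, but SAP 8.5 does not plan percent change for DXA.

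**Mixed units between patients.** Assume 15 patients, all truly at 1.0 g/cm², 3 recorded in kg/m² (value 10) and 12 in g/cm² (value 0.001 after the formula).
- Mean = (3 × 10 + 12 × 0.001)/15 = 30.012/15 ≈ 2.0
- Sample SD = √{[3 × (10 − 2.0008)² + 12 × (0.001 − 2.0008)²]/14} = √(239.95/14) ≈ 4.1
- Correct: mean 10, SD 0.

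**Mixed units within a patient.** With 1.0 g/cm² at baseline and the same density recorded as 10 kg/m² at Visit 6, the SAP's change is 10 − 0.001 = 9.999 kg/m², where the true change is 0.

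**The case against.** The best defence is that the formula names only grams and kilograms, is right for three of the four DXA measures that carry units, and could be read as giving the gram-to-kilogram step with the area step left to the programmer. On that reading the text is incomplete, not wrong. The error also needs a site to record g/cm² and a programmer to apply the formula literally. Nothing in the documents shows that the roughly 3–5 sites use different units, and with one common unit the error is a plain rescaling. A mean density near 0.001 kg/m² looks implausible, and it would pass through the value listing in SAP 8.5 and the sponsor's review of outputs in SAP 13. DXA is descriptive and may be skipped where it is unavailable or the patient does not fit the scanner.

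Much of this stands as a limit on consequence. The wrong values arise only if the text is followed as written, the mixed-unit harm is only possible, and review might well catch it. The defence does not rescue the text. The sentence assigns density to the formula, and even the generous reading leaves no stated route from g/cm² to kg/m². A quiet correction in code would depart from the SAP, and SAP 4 requires such changes to be detailed in the study report.

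One further point is fair: the documents do not say what a density entry in g or kg represents. It may be bone mineral content or a mis-keyed unit, so it should be queried before it is relabelled.

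**Conclusion.** The concern holds. Followed as written, SAP 3.5.2 makes every density recorded in g/cm², and every absolute change derived from such values, too small by exactly 10,000. This rests only on unit definitions and does not depend on the illustrative densities. Values already in kg/m² are unaffected, as are the three masses.

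The uninterpretable pooled mean and SD depend on an assumption the documents permit but do not confirm: that more than one density unit is recorded. The consequence is confined to descriptive DXA output in SAP 8.5 and, through the cross-reference in SAP 10.5, possibly the vital-signs summary. The primary and key secondary endpoints are untouched. It should be corrected because a stated rule gives a wrong reported result and the correction is almost free.

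**What to change.** In SAP 3.5.2:

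1. Restrict kg = g/1000 to total fat mass, lean muscle and total body mass.
2. For bone mineral density, state kg/m² = 10 × g/cm², with entries already in kg/m² left unchanged.
3. Query density entries recorded in g or kg with the site. Keep them out of the density summary and, if confirmed as such, show them separately as bone mineral content.

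The cost is about two lines of SAP text, one line of derivation code and any site queries. Design, sample size and planned assessments do not change.
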